The effect of gluten-free diet on type 1 diabetes (T1D)

NCT02867436

January 10th, 2016

Trial design

This study is a prospective non-randomized intervention trial.

Participants

Study participants were recruited from children patients diagnosed with T1D at inpatient pediatric diabetes clinics at two centers in Prague, Czech Republic (University Hospital Prague-Motol and University Hospital Prague-Královské Vinohrady). Both centers are tertiary care hospitals that annually admit over 65 children patients with newly diagnosed T1D. The recruitment will last from January 2016 to January 2018. Subjects and their parents have the right to withdraw from the study at any time without giving the reason.

Eligibility criteria

Following inclusion criteria will be applied:

- T1D diagnosed according to the ADA criteria [1]
- age 4 – 17.99 years at onset
- positivity of a least one T1D associated antibody (IAA, anti-IA2, anti GAD65)
- presence of high risk HLA-DQB1*03:02-DQA1*03 or DQB1*02-DQA1*05 molecules
- no coeliac disease and negativity of anti-tissue transglutaminase antibodies
- body mass index below +2SD of the age and height standard
- no concomitant disease potentially influencing immune response or gluten sensitivity

Intervention

Subjects in the intervention group will follow strict gluten-free diet while receiving the recommended daily doses of macronutrients. Their meal records for three days prior to the visit will be required for each visit as well as a consultation with nutrition specialist. Adherence to the diet will be tested via the negativity of the gluten immunogenic peptide (GIP) in the commercial iVylisa GIP-S (Biomedal, S.L., Sevilla, Spain) ELISA kit. Stool samples will be tested for GIP presence every 3 months without especially notifying the subjects. Subjects in the intervention arm will receive financial reimbursement for the added cost of gluten-free edibles.

Study procedure

The caregivers of the subjects will sign a written informed consent with the study protocol prior to the enrollment in the first 30 days after T1D diagnosis.

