All subjects will be hospitalized at T1D onset. During the hospitalization, a blood sample will be taken for the measurement of anti-GAD65, anti-IA2 and IAA, glycosylated hemoglobin (HbA1c) (performed by high liquid chromatography) and screening for coeliac disease (total IgA to rule out IgA deficiency anti anti-tissue transglutaminase antibodies analyzed by ELISA test). A stool sample will also be taken for further analysis of their gut microbiome content.

If the subjects fulfill the inclusion criteria, they will be offered to join the trial. The subjects and their parents will choose their study group freely and a mixed-meal tolerance test (MMTT) will be scheduled between 4-8 weeks after T1D onset.

The MMTT is considered a gold standard for the measurement of the endogenous production of residual insulin in subjects with T1D [2]. MMTTs will be performed for all subjects at group allocation and at 6 and 12 months. All subjects will receive a standard liquid meal Ensure Plus (Abbott Laboratories BV, Zwolle, Netherlands) and their C-peptide levels will be measured at the baseline and each 30 minutes up to 150 minutes. All MMTTs will be performed after overnight fasting and children will receive only their evening dose of long-acting insulin analogue. The MMTT will be rescheduled if the subjects' capillary glucose is <3.9 mmol/L (<70 mg/dL) or >10 mmol/L (>180 mg/dL). Serums of subjects from the second center will be transported at $4-8^{\circ}\text{C}$ within 48 hours to the central laboratory. Immediately after the first MMTT, subjects who will choose the intervention group will start with strict gluten-free diet. After the third MMTT at 12 months, subjects and their parents will be allowed to discontinue the diet at their will.

Subjects will be followed up at 3 months intervals. During each visit subjects will undergo a physical examination and their body weight, height and BMI will be measured. Their HbA1c will be measured and their total daily insulin dose noted.

Stool samples will be taken at T1D onset, allocation visit and each 3 months up to 15 months for microbiome analysis and adherence test if the patient belongs to the intervention group. The stool samples will be kept at -80°C until the DNA extraction using the PowerSoil DNA isolation kit (Qiagen, Hilden, Germany). Microbiome profiles will be determined by next-generation sequencing of the V4 variable region of 16S rDNA and processed in a bioinformatic pipeline as described previously [3].

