Blood samples for the measurement of regulatory cell subsets (measured by flow cytometry) and their cytokine profiles (after short term PMA-ionsomycin re-stimulation) will be taken at baseline and at 6 and 12 months.

Intestinal permeability will be measured through serum zonulin (a marker for dysfunctional gut barrier function) levels at baseline and at 12 months [4]. In addition, urine lactulose/mannitol ratio following the ingestion of lactulose/mannitol solution (mannitol g, lactulose g in 100ml water for injection) and 6 hours urine collection [5] will be performed at 12 months (measured using high-performance liquid chromatography).

End points

Primary

- Area under the curve (AUC) of the C-peptide level during the mixed meal tolerance tests

Secondary

- HbA1c
- Insulin requirement (IU/kg)
- Insulin dose adjusted HbA1c (IDAA1c)
- Gut microbiome composition
- Immune parameters (regulatory cell subsets, cytokine production)
- Intestinal permeability (zonulin concentration and lactulose/mannitol urine excretion ratio)

Data collection nad management

All participants will be assigned a study identification number. The forms with patient data will be stored in a locked room with access only to the team of researchers at both centers. Electronic version of data will be kept in password protected databases in accordance with the GDPR legislature.

Statistical analysis

The analysis of the primary outcome will be based on an ANCOVA model with C-peptide AUC at 12 months as a response and the intervention assignment, baseline C-peptide AUC at visit 1, age, gender and body weight as covariates. The tests and confidence intervals will use robust sandwich variance estimator. The primary analysis will follow the per-protocol principle. Secondly, the results at 6 months will also be analyzed. Analyses of secondary outcomes (HbA1c, insulin dose, immune parameters and gut microbiome composition) will proceed by similar methodology. Longitudinal analyses will be performed by linear generalized estimating equation models with a working independence structure. Linear trends in continuous outcomes

over 12 months will be estimated by the intervention arm and compared with adjustment for sex, age, and baseline body weight SDS.

Ethics and dissemination

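### Per-protocol is the only analysis population named, its set is undefined, and no analysis of all children by chosen group is stated to show what exclusions change

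*Combined protocol and SAP*

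**What the plan says.** Under Study procedure, groups are formed by preference: "The subjects and their parents will choose their study group freely". Under Statistical analysis, the primary model is an ANCOVA of 12-month C-peptide AUC on group, baseline AUC, age, gender and weight, with sandwich variance, and "The primary analysis will follow the per-protocol principle". No other population is named anywhere. The 6-month analysis names none, and the secondary outcomes refer back to similar methods. The GEE sentence is also silent on who is included: "Longitudinal analyses will be performed by linear generalized estimating equation models with a working independence structure".

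Adherence is described under Intervention, for the gluten-free group: "Their meal records for three days prior to the visit will be required for each visit", and "Stool samples will be tested for GIP presence every 3 months without especially notifying the subjects". Study procedure confirms the restriction. Stool is collected from everyone, but the samples are used "for microbiome analysis and adherence test if the patient belongs to the intervention group".

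No section links a GIP result or a meal record to membership of the per-protocol set. Ethics and dissemination says that all deviations are monitored and recorded, for safe conduct, and gives them no role in the analysis. The outcome itself is planned for everyone: "MMTTs will be performed for all subjects at group allocation and at 6 and 12 months".

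**The concern.** A per-protocol set is defined by what happens after baseline. Here the plan does not say how many positive GIP tests exclude a child, or how missing stool samples and missing meal records count. Families know their group, and no text says when the set is fixed.

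Because the two adherence checks apply to one arm, exclusions that rest on them would remove children from that arm alone. If children who adhere poorly also differ in 12-month C-peptide for reasons other than gluten, the diet arm that remains is a selected group and the control arm is not selected in the same way. Covariates measured at baseline do not undo this.

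What is at stake is whether the primary estimate can be interpreted. With only a per-protocol result, a reader cannot tell a diet effect from the effect of who was left out.

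**Working it through.** **No figure to reproduce.** The documents give no sample size, alpha, SD, dropout rate or GIP-positive rate. The textual part of the check is the comparison of sections above. What follows only illustrates scale, and every input is an assumption.

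**Inputs (assumed).** There is no true diet effect and no confounding. The diet arm has four quarterly GIP tests over the 12 months. Each child has a standardised adherence trait *A* (higher means better adherence). *r* is the correlation of *A* with the covariate-adjusted 12-month AUC. *p* is the chance that a sample is positive, and ρ is the within-child correlation of the tests. The values *p* = 0.054 and 0.085 give about 20% and 30% of children with any positive if tests are independent: 1 − 0.946⁴ = 0.199 and 1 − 0.915⁴ = 0.299.

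**Model.** Each test has liability −√ρ·*A* + √(1−ρ)·*e* and is positive above the 1−*p* normal quantile. Bias in residual SD is *r* × E[*A* | kept], found by numerical integration.

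| *p* | ρ | Excluded, any positive | Bias, *r*=0.3 | Bias, *r*=0.5 | Excluded, two or more | Ratio of exclusions |
|---|---|---|---|---|---|---|
| 0.054 | 0 | 19.9% | 0 | 0 | 1.6% | 12.2 |
| 0.054 | 0.3 | 17.5% | 0.062 | 0.103 | 3.4% | 5.1 |
| 0.054 | 0.5 | 15.4% | 0.068 | 0.113 | 4.5% | 3.4 |
| 0.054 | 0.7 | 12.9% | 0.065 | 0.109 | 5.4% | 2.4 |
| 0.085 | 0 | 29.9% | 0 | 0 | 3.9% | 7.7 |
| 0.085 | 0.3 | 25.8% | 0.087 | 0.146 | 6.6% | 3.9 |
| 0.085 | 0.5 | 22.6% | 0.094 | 0.157 | 8.0% | 2.8 |
| 0.085 | 0.7 | 19.0% | 0.091 | 0.151 | 8.9% | 2.1 |

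Example: at *p* = 0.085 and ρ = 0.5, E[*A* | kept] = 0.315, so bias is 0.3 × 0.315 = 0.094 or 0.5 × 0.315 = 0.157. At *r* = 0.1 the largest value is 0.031. If two or more positives are needed, the largest bias is 0.049 at *r* = 0.3 and 0.082 at *r* = 0.5.

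**Against sampling error.** With an assumed 40 per arm and 22.6% of the diet arm excluded, the standard error is √(1/40 + 1/(40 × 0.774)) = 0.24 SD. A bias of 0.094 is 0.39 of that, and 0.157 is 0.66.

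**Rejection rates.** These come from simulating the planned ANCOVA with a sandwich variance (4000 runs per cell, 25, 40 and 65 per arm, nominal 5%, *p* = 0.085, ρ = 0.5, any positive excludes). Per-protocol rejection was 6.0, 8.0 and 7.8% at *r* = 0.3, and 7.3, 11.1 and 13.3% at *r* = 0.5. Over all simulated cells, analysis by chosen group with complete 12-month tests gave 4.0-5.8% and bias within 0.01 SD. If half the GIP-positive children lacked the 12-month test, the by-chosen-group bias at *p* = 0.085 and ρ = 0.5 was about 0.04 SD at *r* = 0.3 and 0.07 at *r* = 0.5.

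**The case against.** Per-protocol is a legitimate question for a strict-diet trial. Controls have no prescribed diet, so testing only the diet arm follows from the design. The trial is not randomised, so an analysis by chosen group has no randomisation to preserve, and a nominal 5% error rate is not guaranteed for any analysis set. All of this stands. The point is the missing rule and the missing companion analysis. It is not an objection to the testing or to the per-protocol label.

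The magnitude is also wholly assumed, and at *r* = 0.3 the bias is under half a standard error at 40 per arm. That stands too: the effect may be negligible.

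Four stronger readings are tempting, and the documents do not support them.

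- A reader might infer that any exclusion for dietary non-adherence can fall only on the gluten-free arm. Deviations are monitored without restriction to one arm, and all children are seen every 3 months, so a control child who took up the diet could be recorded. Withdrawals can occur in either arm.
- A reader might infer that a GIP-positive child is excluded. The text does not say so.
- A reader might infer that the bias favours the diet. That needs poor adherers to have lower adjusted C-peptide for reasons other than gluten, and nothing in the documents shows this.
- A reader might infer that the set will be chosen after outcomes are known. The plan is silent on timing, which leaves this open but does not show it.

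**Conclusion.** The gap is real and should be fixed; confidence is medium. That per-protocol is the only population named, that its set is undefined, and that no analysis of all children by chosen group is stated are all matters of text and are certain. The size and direction of any bias are not established.

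On the assumptions above, excluding on any positive test drops 13-30% of the diet arm, with bias of 0 to 0.09 residual SD at *r* = 0.3 and 0 to 0.16 at *r* = 0.5. It is zero at *r* = 0 and changes sign if *r* is negative. Requiring two or more positives drops 2-9%. The choice of rule therefore changes the excluded fraction 2- to 12-fold, depending on the within-child correlation. The largest ratios occur at zero correlation, where the bias is zero, so the ratio alone does not measure harm.

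**What to change.** Add the same ANCOVA on all enrolled children with a visit-1 mixed-meal test, by the group they chose and regardless of GIP results or meal records, and report it beside the per-protocol result. Seek the 12-month test, already planned for everyone, from children who stop the diet. Report exclusions with reasons, and missing 12-month tests, by group.

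As part of the same change, and before outcomes are seen, fix the per-protocol rule: how many positive GIP tests exclude a child, and how missing stool samples and meal records count. State the population for the GEE models. Which analysis is labelled primary remains the sponsor's choice of question.

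The cost is a short paragraph, one more model run, and the effort of bringing back families who stopped the diet. It needs no new patients, visits or tests. The downside is that the by-chosen-group estimate includes non-adherers and may be smaller. Exclusions based on GIP or meal records would still be one-sided in the per-protocol result; the added analysis only shows how much they matter. It does not remove confounding from self-selection or bias from missing 12-month tests.

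### Do the microbiome and immune outcomes need a named response and false-discovery control before the plan can stand?

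*Combined protocol and SAP*

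**What the plan says.** The primary model is given in the Statistical analysis section: "ANCOVA model with C-peptide AUC at 12 months as a response and the intervention assignment, baseline C-peptide AUC at visit 1, age, gender and body", the last covariate being body weight. So there is one continuous response adjusted for its own baseline. "The tests and confidence intervals will use robust sandwich variance estimator". The section continues, "Secondly, the results at 6 months will also be analyzed", and then extends the approach: "Analyses of secondary outcomes (HbA1c, insulin dose, immune parameters and gut microbiome composition) will proceed by similar methodology". It also plans GEE models that compare linear trends in continuous outcomes between arms.

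Under End points, gut microbiome composition and immune parameters are listed as secondary, with no further status. Under Study procedure, the immune measurements are "regulatory cell subsets (measured by flow cytometry) and their cytokine profiles", taken at baseline, 6 and 12 months and not itemised. For the microbiome, "Stool samples will be taken at T1D onset, allocation visit and each 3 months up to 15 months". Profiles come from sequencing the V4 region of 16S rDNA, processed by a pipeline for which the protocol cites a publication. Group membership is self-selected: "The subjects and their parents will choose their study group freely".

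The document gives no significance level, sample size, number of tests or multiplicity rule for any end point.

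**The concern.** An ANCOVA needs one number per child at follow-up and the matching number at baseline. A microbiome profile is a composition of many taxa, so the model cannot be run until someone chooses a diversity index, a set of taxa, a transformation or some other summary. Two stool samples are taken before the diet starts, and the text does not say which of them is the baseline.

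The immune outcomes fit the model one marker at a time, but the markers are neither listed nor counted. A direct reading of a similar method for a multi-feature outcome is one test per feature. Nothing says that such tests will be adjusted or treated as exploratory, and the 6-month and trend analyses add to their number.

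At stake is the reading of secondary results. Some taxa or markers with no true difference could be reported as group differences, and the response could be chosen after the data are seen.

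**Working it through.** **What can be settled from the text**

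1. *Baseline stool sample.* The primary model takes its baseline at visit 1. Study procedure places the first MMTT at group allocation, starts the diet immediately after it, and schedules a stool sample at the allocation visit. Carrying the same approach over to the microbiome therefore points to the allocation sample, which is also the last one before the diet. The onset sample belongs to the initial hospital stay. This is a small matter of wording.
2. *Response.* No section names one. The cited pipeline is described as processing sequence data, and the publication is not available here, so it cannot be credited with defining a response.
3. *Feature-by-feature testing.* It is not stated. The plan says similar methodology, not identical, which allows a scalar summary, transformed abundances, or both.
4. *Status.* These outcomes are called secondary and nothing more. There is no alpha allocation, no hierarchy and no claim of confirmation that uncontrolled testing would undermine.

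**Scale if tests were run feature by feature**

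The plan gives no figure to reproduce. The inputs below are all assumed: two-sided 5% per test, the number of tests *m*, the correlations, the effect size and the group sizes.

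*Chance of at least one false positive when nothing differs.* For independent tests this is 1 − 0.95^*m*. For equicorrelated normal statistics it comes from integrating over the shared component.

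| *m* | independent | correlation 0.5 | correlation 0.8 |
|---|---|---|---|
| 5 | 1 − 0.95^5 = 23% | 18% | 13% |
| 20 | 1 − 0.95^20 = 64% | 42% | 22% |

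The expected number of false positives is 0.05 × *m* whatever the correlation: 0.25 for 5 tests and 1 for 20.

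*Price of adjusting.* Take 20 features, 2 of which truly differ by 0.8 SD, with baseline correlation 0.5 and between-feature correlation 0.3. The residual SD is √(1 − 0.5²) = 0.866. The standard error of the group difference is 0.866 × √(2/*n*), which is 0.274 for *n* = 20 per group and 0.194 for *n* = 40. The ratios of effect to standard error are 0.8/0.274 = 2.92 and 0.8/0.194 = 4.13. On an ordinary t test that ignores the precision lost to the extra covariates, power per feature is about 82% and 98%.

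Simulating the full six-parameter ANCOVA with the HC3 sandwich and a t reference gives:

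| per group | power, unadjusted | power, Benjamini-Hochberg | mean false share of reported differences, unadjusted | the same, Benjamini-Hochberg |
|---|---|---|---|---|
| 20 | 70% | 29% | 22% | about 3% |
| 40 | 97% | 83% | 19% | about 3% |

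Of 2 true effects, the expected number found falls from 2 × 0.70 = 1.40 to 2 × 0.29 = 0.58 at 20 per group, and from 2 × 0.97 = 1.94 to 2 × 0.83 = 1.66 at 40. In return, the false share drops by about 19 points (22 − 3) at 20 per group and 16 points (19 − 3) at 40. With small groups, that is a real exchange of missed findings for fewer chance findings.

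**The case for a change.** The strongest case for a change is that the microbiome analysis, as written, cannot be run. Someone must choose the response, and without a prior choice it may be made with the results in view. Secondary outcomes may reasonably go without multiplicity control, but then an exploratory label is expected, and the plan has neither. Readers could adjust for themselves only if every test were reported, which is not promised. The remedy would be a few lines of text with no new samples.

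The textual facts stand: there is no response, no marker list and no label. A publication that picks out individual taxa or cytokines should state how many were tested. What does not follow is that the plan is wrong. The smallest remedy is only naming and labelling, which an analyst of 16S data would supply in the ordinary course, together with false-discovery adjustment across taxa. The larger remedy, mandatory Benjamini-Hochberg across secondary immune markers, is a preference, and a costly one if groups are small. Neither touches the larger limit on interpretation, that families choose the diet: multiplicity control removes chance findings and leaves confounding in place.

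The type of sandwich estimator also matters for error rates in small samples. In simulations with 99 null taxa on a log-ratio scale and 20 children per group, the uncorrected form with normal quantiles rejects about 8% and HC3 about 3 to 4%. But that question applies equally to the primary C-peptide model and is separate from this one.

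**Conclusion.** No change is called for. The plan is thin on the microbiome and immune outcomes, but this is missing detail of a kind that analysts fill sensibly, combined with a fair trade-off over multiplicity. The baseline can be read from the visit schedule, and nothing in the text requires unadjusted testing of every feature or presents these outcomes as confirmatory.

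If features were tested one by one without adjustment, the chance of at least one false positive among 20 null tests would lie between 22% (correlation 0.8) and 64% (independence). Adjustment would cost about 41 points of power per feature at 20 children per group (70 − 29) and 14 points at 40 (97 − 83). These figures depend on an assumed 5% level, 20 features, 2 effects of 0.8 SD and the stated correlations; the documents give none of them. Multiplicity here bears only on how secondary results are read, and the primary 12-month C-peptide test is unaffected by it.

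### The GEE trend comparisons of HbA1c, insulin requirement and IDAA1c leave out visit-1 C-peptide AUC; if the self-chosen arms differ in it and it predicts change, the slope contrast is biased

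*Combined protocol and SAP*

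**What the plan says.** All references are to the combined protocol and SAP.

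- **Allocation.** Trial design: "This study is a prospective non-randomized intervention trial". Study procedure: "The subjects and their parents will choose their study group freely".
- **Visit-1 C-peptide.** Study procedure calls the MMTT a "gold standard for the measurement of the endogenous production of residual insulin in subjects with T1D" and schedules it for everyone: "MMTTs will be performed for all subjects at group allocation and at 6 and 12 months". The order is explicit: "Immediately after the first MMTT, subjects who will choose the intervention group will start with strict gluten-free diet". On the planned schedule, the visit-1 AUC is therefore a pre-treatment value.
- **Primary model.** Statistical analysis: the 12-month AUC is regressed on arm and "baseline C-peptide AUC at visit 1, age, gender and body weight as covariates".
- **Secondary outcomes at 6 and 12 months.** The same section says only that they are handled in a similar way. It names no covariates, and its list in brackets does not include IDAA1c.
- **Trend models.** For any continuous endpoint, the slopes "over 12 months will be estimated by the intervention arm and compared with adjustment for sex, age, and baseline body weight SDS". The method of fitting is a linear GEE with working independence. The covariate list is complete as written and does not contain C-peptide AUC. Nothing elsewhere adds it, and no propensity or sensitivity analysis for confounding is described.

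**The concern.** Without randomization, covariate adjustment is the plan's only protection against arms that differ at the start. Residual insulin secretion is an obvious candidate for such a difference. It is plausible that a child's reserve at 4 to 8 weeks bears on how insulin dose, HbA1c and IDAA1c move over the year. The plan measures that reserve before the diet and uses it for the primary endpoint, but leaves it out of the trend comparisons of the clinical endpoints.

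At stake is the reading of a positive secondary result. A flatter rise in dose or HbA1c in the gluten-free arm could reflect better starting reserve rather than the diet, and the planned trend model could not tell the two apart. If AUC is prognostic for slope, some precision is lost as well.

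**Working it through.** The documents give no sample size, SD, correlation or arm difference, so there is no stated figure to reproduce. All sizes below rest on assumptions.

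**1. When the slope contrast is biased.** Let d be the arm gap in visit-1 AUC (in SD) and g the reduction in an outcome's yearly slope per SD of AUC. With no diet effect, a trend model without AUC gives an arm-by-time contrast of about -g x d. A gap that moves only the level of the outcome goes into the arm intercept and cancels. If g = 0 or d = 0 there is no bias.

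**2. Size under moderate correlations.** Assumptions, for a standardised outcome:

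- correlation of AUC with the 12-month value: c = -0.3 to -0.5
- correlation of AUC with the visit-1 value: a = -0.2 to -0.3
- correlation of the visit-1 and 12-month values: r = 0.4 to 0.5
- d = 0.2 to 0.4; 60 to 100 children, 1:1; no diet effect

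Taking the 0-to-12-month change as a proxy for slope, the implied correlation of AUC with change is (c - a)/sqrt(2(1 - r)).

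- Smallest: c = a = -0.3 gives 0.
- Largest: c = -0.5, a = -0.2, r = 0.5 gives -0.3/1 = -0.30.

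In SD of change, the bias is correlation x d and the standard error is about 2/sqrt(n). At the largest correlation:

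| n | d | bias | SE | bias/SE | false rejection |
|---|---|---|---|---|---|
| 100 | 0.4 | 0.12 | 0.200 | 0.60 | 9.2% |
| 60 | 0.4 | 0.12 | 0.258 | 0.46 | 7.5% |
| 100 | 0.2 | 0.06 | 0.200 | 0.30 | 6.0% |

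False rejection is Phi(-1.96 + z) + Phi(-1.96 - z), with z = bias/SE. At the smallest correlation it is 5%.

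**3. Simulation of the planned model.** Linear GEE, working independence, sandwich variance; complete visits at 0, 3, 6, 9 and 12 months; no diet effect; 600 runs per setting. Assumed: random-intercept SD 0.8, random-slope SD 0.5, error SD 0.6, and a starting level that falls by 0.5 per SD of AUC. The two figures in each rejection cell are for 20 and 40 children per arm.

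| d | g | -g x d | mean contrast, planned | rejection, planned | rejection, AUC + AUC x time |
|---|---|---|---|---|---|
| 0.5 | 0 | 0 | 0.00, 0.00 | 5.7%, 5.2% | 6.5%, 5.7% |
| 0.3 | 0.3 | -0.09 | -0.08, -0.08 | 7.3%, 4.8% | 7.2%, 2.8% |
| 0.5 | 0.3 | -0.15 | -0.17, -0.14 | 11.0%, 9.3% | 7.0%, 7.5% |
| 0.5 | 0.5 | -0.25 | -0.26, -0.24 | 13.5%, 18.8% | 6.8%, 4.7% |
| 0.8 | 0.5 | -0.40 | -0.40, -0.41 | 23.3%, 44.0% | 7.8%, 7.7% |

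With AUC x time included, the mean contrast lies between about -0.02 and +0.03 in every setting run. The Monte Carlo standard error near 5% is sqrt(0.05 x 0.95/600) = 0.9 percentage points, and the sandwich variance is somewhat liberal in samples this small.

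**4. Linking steps 2 and 3.** For these five visits the sum of squares of time is 0.625, so a child's fitted slope has error variance 0.36/0.625 = 0.576. The correlation of AUC with the fitted slope is g/sqrt(0.25 + g^2 + 0.576), which is 0.31 at g = 0.3 and 0.48 at g = 0.5. The g = 0.3 rows thus match the top of the range in step 2. The g = 0.5 rows need a stronger relation than those correlations imply.

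**5. A main effect is not enough.** Adding AUC without AUC x time gave the same contrast and the same rejection rate as the planned model in every setting. With balanced visits and working independence, a time-constant covariate does not touch the arm-by-time term.

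**6. The 6- and 12-month ANCOVAs.** If the secondary ANCOVAs replace visit-1 AUC with the outcome's own baseline, the bias is (c - a x r) x d. With c = -0.5, a = -0.3, r = 0.5, d = 0.4 this is (-0.5 + 0.15) x 0.4 = -0.14 SD. With n = 100 the SE is 2 x sqrt(0.75/100) = 0.173, and false rejection is about 12.8%. If they keep visit-1 AUC, the issue does not arise. The text allows either reading.

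**The case against.** The strongest case against is that both conditions are unproven. The documents say that the MMTT measures residual insulin; they do not say that it predicts the course of HbA1c or dose. Nor do they say that families know the AUC when they choose: the group is chosen and the first MMTT is then scheduled. Choice could follow AUC only through correlates, and age, sex and weight are already in the model. The gap that matters is the one left after those covariates, and no document supports a particular value. All of this stands, and it is why the point is conditional. One qualification is that, by step 5, age, sex and weight protect the slope contrast only if they too enter with time interactions, which the plan does not state.

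A reader might infer three stronger things that the documents do not support:

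- **Any starting difference in residual insulin would appear as a diet effect.** It would not; a pure level difference cancels in the slope contrast.
- **Chance imbalance causes false positives.** Across repetitions it is already covered by the nominal error rate. It costs precision but is not systematic bias.
- **The trend test could run at about 17% with 100 children and a gap of 0.4 SD.** That needs a correlation of 0.5 between AUC and slope (bias/SE = 0.5 x 0.4/0.2 = 1.0). The correlations in step 2 imply 0.30 at most.

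It is also fair that the ANCOVA part rests on an ambiguous sentence, so it is a request for clarification and not a demonstrated omission.

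**Conclusion.** The point holds in conditional form. The omission of visit-1 AUC from the trend models is explicit. It matters if the arms differ in AUC beyond age, sex and weight, and AUC predicts change in the outcome. The bias is then about the gap times the AUC effect on slope.

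Under the moderate correlations assumed here, false rejection is about 5% to 9% with 100 children and a gap of 0.4 SD, and 5% to 6% with a gap of 0.2 SD. It is higher only if AUC predicts slope more strongly or the gap is larger, as in the last two rows of the simulation. These figures assume linear effects and complete visits, and none of the inputs comes from the documents.

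The primary ANCOVA is not affected, since it already contains visit-1 AUC. It would also be wrong to infer that this adjustment makes the secondary comparisons causal: it removes one measured imbalance and leaves other consequences of family choice.

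**What to change.** In the Statistical analysis section:

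1. Add visit-1 C-peptide AUC and its interaction with time to the GEE trend models for HbA1c, insulin requirement and IDAA1c. Name both terms, because the main effect alone leaves the slope contrast unchanged.
2. State that the 6- and 12-month ANCOVAs of these three endpoints include both visit-1 AUC and the outcome's own baseline, and name IDAA1c among the outcomes analysed.

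The cost is two extra terms in each trend model, at most one more in each ANCOVA, and a sentence or two of text. The MMTT is already scheduled for every child, so no new data are needed; a child with a missing or failed visit-1 test would need a stated rule. Naming the terms before analysis also prevents covariates being chosen after the results are seen.
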